#### 8.4 Time Period for Reporting AE and SAE

For each patient the standard time period for collecting and recording AE and SAEs will begin at day 1 when the first capsule is administered and will continue until 30 days after the end of study visits at day 90. Patients will be asked about side effects, and specifically flushing, at all points of contact with the investigator.

During the course of the study all AEs and SAEs will be proactively followed up for each patient; events should be followed up to resolution, unless the event is considered by the investigator to be unlikely to resolve due to the underlying disease. Every effort should be made to obtain a resolution for all events, even if the events continue after discontinuation/study completion.

#### 8.5 Recording of Adverse Events

SE and SAE will be recorded on SA/SAE forms and evaluated according to CTCAE criteria. Any unexpected laboratory value or vital sign will also be recorded as an AE. The CTCAE system will be used to identify levels of abnormality that require reporting. Related clinical signs and symptoms must be noted. Abnormal laboratory results/vital signs will be considered additional information if related to a symptom, sign or diagnosis that warrant reporting on it's own.

The following information will be noted in the AE/SAE forms:

- Dose, way of administration and duration of treatment.
- The nature of the event(s) will be described by the investigator in precise standard medical terminology (i.e. not necessarily the exact words used by the patient).
- The duration of the event will be described in terms of event onset date and event ended data.
- The result of the AE/SAE (Death, life threatening, not yet resolved/still treated for SAE/AE, treated and resolved, improved with sequelae, resolved without sequelae).
- The grade (1-5) according to the CTCAE system.
- The Causal relationship of the event to the study medication will be assessed as one of the following (the definitions below are according to WHO):

#### **Unrelated:**

There is not a temporal relationship to investigational product administration (too early, or late, or investigational product not taken), or there is a reasonable causal relationship between non-investigational product, concurrent disease, or circumstance and the AE.

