#### **8.2 Expected Adverse Events**

Previous studies have showed that NR in general is well tolerated. In a 2019 study of healthy, obese individuals it was found that type, incidence and severity of AE were similar across the different intervention groups and the placebo group. (Conze, D., Brenner, C. & Kruger, C.L. Safety and Metabolism of Long-term Administration of NIAGEN (Nicotinamide Riboside Chloride) in a Randomized, Double-Blind, Placebo-controlled Clinical Trial of Healthy Overweight Adults. Sci Rep 9, 9772 (2019). https://doi.org/10.1038/s41598-019-46120-z)

There were no statistically significant differences in the NIAGEN and placebo-groups with respect to any clinical chemistry parameter either, and no serious AE or reports of flushing were registered. Importantly, all AEs were resolved by the end-of-study.

No other animal- or human studies published have demonstrated any serious side effects of NR. In a study (reference 17 in the protocol) from 2017 there were no significant differences in the incidence of AEs in the intervention group compared to the placebo group. In the intervention group, six adverse events (mild nausea, moderate fatigue, mild headache, moderate dyspepsia, moderate abdominal discomfort and moderate diarrhoea) were possibly related to NR. All participants reporting AEs recovered and there were no SAEs reported in this clinical study either.

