#### **Unlikely:**

There is a temporal relationship to investigational product administration, but there is not a reasonable causal relationship between the investigational product and the AE.

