#### Possible:

There is reasonable causal relationship between the investigational product and the AE. Dechallenge information is lacking or unclear.

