#### Probable:

There is a reasonable causal relationship between the investigational product and the AE. The event responds to de-challenge. Re-challenge is not required.

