7.1 Adverse Events

Adverse events were registered at each point of contact with the patient. Additionally, some adverse events were recorded after a participant made contact or if the investigator otherwise was made aware of any adverse event. Both adverse events reported by the patient and those recorded in hospital records, are registered.

Adverse events were recorded according to an event reporting system (Common Terminology Criteria for Adverse Events (CTCAE version 5.0)). The investigator graded each AE accordingly using the levels mild, moderate severe, life threatening or leading to death. For tabulations, only treatment emerging adverse events (TEAEs) will be presented. TEAEs are defined as AEs with a start date on or after date of first randomised treatment. Any AEs prior to treatment will be listed but not tabulated.

The number (%) of subjects with any TEAEs, with 1, 2 or > 3 TEAEs, with treatment related TEAEs, with treatment emerging serious AEs (TESAE) and TEAEs leading to study drug withdrawal will be summarized by treatment group. The number of events and number (%) of subjects with adverse events by system organ class (SOC) and preferred term (PT) will be summarized by treatment group, overall, for severe AEs and for AEs leading to study discontinuation.

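### The causality categories in Protocol 8.5 overlap, so an event with both NR and another reasonable cause can be rated Unrelated and left out of the treatment-related summary

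*Protocol*

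**What the plan says.** Protocol 8.5 wants a single rating per event: "The Causal relationship of the event to the study medication will be assessed as one of the following". Five categories follow, attributed to WHO.

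- **Unrelated** has two limbs joined by *or*. One is the absence of a temporal link. The other reads "or there is a reasonable causal relationship between non-investigational product, concurrent disease, or circumstance and the AE".
- **Unlikely** has a temporal link, but NR is judged not to be a reasonable cause.
- **Possible** is worded as follows: "There is reasonable causal relationship between the investigational product and the AE. Dechallenge information is lacking or unclear".
- **Probable** requires NR to be a reasonable cause and adds: "The event responds to de-challenge. Re-challenge is not required".
- **Definite** requires NR to be a reasonable cause and adds no further criterion.

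No sentence says which category prevails when an event fits more than one.

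The rating is used in two places. SAP 7.1 plans to report, by arm, the subjects "with treatment related TEAEs", without saying which of the five ratings count as related. Protocol 8.7.1 requires notice to the safety committee within one day for an SAE rated probably or definitely related, and within four days for any SAE.

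**The concern.** The second limb of Unrelated asks only whether something else could reasonably have caused the event. It does not ask whether NR could have caused it too. In hospital patients recovering from tissue damage, an underlying illness or another drug will often be a reasonable cause, so the limb is easily met.

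Protocol 8.2 shows the kind of event at risk. It lists six mild or moderate events from a 2017 study: nausea, fatigue, headache, dyspepsia and, to end the list, "moderate abdominal discomfort and moderate diarrhoea) were possibly related to NR". All six are symptoms that can also be put down to illness or to other drugs.

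At stake is the treatment-related row of the safety report, in a trial whose SAP names the assessment of NR adverse events as a secondary objective. For non-serious events the documents describe discussion at weekly meetings and fortnightly updates to the committee, but no second causality rating. The investigator's category therefore goes straight into the table.

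**Working it through.** The plan states no figure to reproduce. The check is to apply the five definitions as written to every combination of conditions.

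**Inputs (Protocol 8.5).** Is there a temporal link? Is another cause reasonable? Is NR a reasonable cause? Is dechallenge unclear, positive or negative?

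**Step 1: events with a temporal link.**

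| Another cause reasonable | NR reasonable | Dechallenge | Categories met |
|---|---|---|---|
| yes | yes | unclear | Unrelated, Possible, Definite |
| yes | yes | positive | Unrelated, Probable, Definite |
| yes | yes | negative | Unrelated, Definite |
| yes | no | any | Unrelated, Unlikely |
| no | yes | unclear | Possible, Definite |
| no | yes | positive | Probable, Definite |
| no | yes | negative | Definite |
| no | no | any | Unlikely |

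Without a temporal link, and taking it that NR is then not a reasonable cause, only Unrelated is met.

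**Step 2: reading the table.** All three rows with two reasonable causes meet Unrelated and at least one related category. Because Definite has no criterion of its own, the same event can be put at either end of the scale. The Unrelated/Unlikely overlap in the fourth row matters less, since NR is not a reasonable cause there.

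**Step 3: consequences by type of event.**

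- *Non-serious events.* A two-cause event rated Unrelated leaves the treatment-related summary in SAP 7.1. It stays in the tables of any TEAE and of events by system organ class and preferred term, which ignore causality.
- *SAEs otherwise rated Possible.* No change in committee timing, because Possible does not trigger the one-day notice.
- *SAEs otherwise rated Probable or Definite.* If rated Unrelated, the committee deadline moves from one day to four.

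**Step 4: size.** The number lost is the number of two-cause events that assessors chose to rate Unrelated. It can lie anywhere between none and all of them. The documents give neither the frequency of such events nor the assessors' practice, so no estimate is possible.

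**The case against.** A reader might infer three stronger things, and the documents support none of them.

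*That the rule forces Unrelated.* It does not. The same event also meets a related category, and nothing gives Unrelated precedence. The text permits the loss; it does not impose it.

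*That suspected reactions drop out of expedited reporting.* Every SAE reaches the committee within four days whatever its rating, and Protocol 8.7.1 has the committee make its own evaluation of causality and expectedness. The SUSAR definition in Protocol 8.1.3 needs a relation to the product but is not tied to the five categories. The examples in Protocol 8.2 come from a study without SAEs, so they bear on non-serious events only.

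*That nearly every event has another reasonable cause.* Patients enter when medically stable, and Protocol 4.4 excludes unstable ones. Events are collected from the first capsule to 30 days after the day-90 visit (Protocol 8.4), nominally 90 + 30 = 120 days. The assumed median stay is 15 days (Protocol 10.1), which leaves 120 − 15 = 105 days after discharge for a typical patient. Other causes will be common, but how common is unknown.

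It can also be said that the assessors are blinded, so the same rule applies to NR and placebo, and that the all-causality tables remain. Both points are right, and they limit the harm. They do not restore the related count: if the same share were dropped in both arms, the ratio would hold, but each count and the absolute difference would shrink in proportion.

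The attribution to WHO does not settle the matter. The source is not available here, and the overlap is in the protocol's own text either way.

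**Conclusion.** The defect is real and should be corrected, but it is narrow. The five categories are not mutually exclusive, and an event with both NR and another reasonable cause can be rated Unrelated. The exposed output is the treatment-related summary in SAP 7.1, chiefly for non-serious events. That summary is doubly undefined, because the SAP does not say which ratings enter it. For SAEs the effect is at most a committee deadline of four days in place of one, for events that would otherwise be Probable or Definite. The primary analysis and the all-causality safety tables are not affected.

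The conclusion rests on the wording of the definitions and on one judgement: that in this population another reasonable cause will often be present. The documents do not allow the loss to be quantified.

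**What to change.** 1. In Protocol 8.5, change the second limb of Unrelated to: *or another cause explains the event and a contribution of the investigational product is not reasonable*.
2. Add to Possible: *this includes events that could also be explained by concurrent disease or other drugs*.
3. Give Definite a criterion that separates it from Possible and Probable. Say also where an event with a reasonable NR cause and negative dechallenge belongs, since only Definite covers it now among the related categories.
4. In SAP 7.1, state which ratings count as treatment related. If neither Unrelated nor Unlikely counts, the remaining overlap between those two does not affect the table.
5. Re-read, while still blinded and before database lock, the events rated Unrelated on the other-cause limb. SAP 7.1 describes event recording in the past tense, so this step may carry most of the benefit.

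The cost is a few phrases in each document, the re-rating work, and ethics committee approval of the protocol change (Protocol 11.4). Protocol 10.4 allows the statistical plan to be amended until the day of database lock. The downside is a somewhat higher count of possibly related events in both arms.

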#### **Unlikely:**

There is a temporal relationship to investigational product administration, but there is not a reasonable causal relationship between the investigational product and the AE.

#### Possible:

There is reasonable causal relationship between the investigational product and the AE. Dechallenge information is lacking or unclear.

#### Probable:

There is a reasonable causal relationship between the investigational product and the AE. The event responds to de-challenge. Re-challenge is not required.

#### Definite:

There is a reasonable causal relationship between the investigational product and the AE.

#### Action taken:

The outcome of the adverse event:

- Has the event resolved or is it still on-going?
- Make note of treatments and investigations carried out.
- Record if the study drug has been continued or not.

#### 8.7 Reporting Procedure

#### 8.7.1 AEs and SAEs

SE are to be recorded in the study's own forms and the SMC (Safety Monitoring Committee) will be updated every forth night. AE/SAE will be discussed at the study's weekly meetings. The SMC should be informed of any SAE at the earliest convenience and no later than 4 days. If the SAE is considered to be either probably or definitely related to the study drug, the SMC must be informed within 1 day.

The leader of the SMC, [name], will receive the report in the form of a password protected excel sheet that is available on K:sensitive, see example below:

#### AE and SAE in the B3Short study:

| Pasient ID og  | Alder/kjønn | Spurt  | Inklusjonsdato | Andre     | Dato for | SAE | AE |
|----------------|-------------|--------|----------------|-----------|----------|-----|----|
| hoveddiagnoser |             | om AE? |                | relevante | AE/SAE   |     |    |
|                |             |        |                | medisiner |          |     |    |

| Gradering | Konsekvens | Ekstra ved
SAE:
Dødsårak,
obduksjon, | info | Sammenheng med studiemedisin? | Studiemedisinen er: |
|-----------|------------|---|------|-------------------------------|---------------------|
|           |            | obuuksjoii,                                   |      |                               |                     |
|           |            | SUSAR?  |      |                               |                     |

The head of the Department of Microbiology (where PI and PhD candidate are employed), Doctor [name] will be the recipient of reports in the Achilles system.

The study safety committee keeps detailed records of all SAEs reported by the investigators and performs an evaluation with respect to causality and expectedness. Based on, among other, SAE reports the sponsor will evaluate whether the risk/benefit ratio associated with the study has changed.

#### **8.7.2 SUSARs**

SUSARS will also be recorded in the hospital's own reporting system (Achilles). If the seriousness of the SUSAR is exceeding the expected risk in similar scenarios, the OUS Department of Quality and patient safety will be contacted for a discussion no later than 24 hours after the event ([contact]. If deemed necessary, the allocation code can be broken and the Norwegian Board of Health Supervision notified as appropriate.

#### 8.8 Procedures in case of emergency

Medical emergencies will be taken care of by the treating physician present at the hospital at all times. An unblinding procedure follows below. This procedure will be available at the ward (see also chapter 9.2). The investigators will also be available by phone at all times and concerning any study-related question.

The investigators ([name] ph. no [name] (investigator) and [name] ph. no [name] (primary investigator)) are responsible for assuring that there are procedures and expertise available to cope with emergencies during the study.

Every effort should be made to contact the investigators before unblinding. Unblinding is permissible when the treatment of the patient is dependent on whether the patient was given NR or not. For information regarding code breaking, please see section 9.2.3 Envelopes are kept at the medical ICU at OUS ([contact]) and each has a kit number written on the outside. The corresponding kit number is also recorded in DIPS to allow hospital staff to identify the correct envelope.

#### **Details of un-blinding procedure:**

In case of need for emergency un-blinding the study staff will be contacted by the doctor requesting un-blinding. If un-blinding is deemed necessary, this will be done by opening of the envelope belonging to the patient who will be kept in the medical ICU at Ullevål hospital which always has staff on duty. The date and time of un-blinding must be documented in the eCRF and in the patient's hospital records.

In the event of an SAE, the Investigator may only break the treatment code if the appropriate future management of the patient necessitates knowledge of the current treatment. Although it is advantageous to retain the blind for all patients prior to final trial analysis, when an SAE may be a serious adverse reaction unexpected or otherwise judged reportable on an expedited basis, it is recommended that the blind should be broken only for that specific patient, by an independent person in the Clinical Trials Unit or its designee, even if the Investigator has not broken the blinding.

#### 8.9 Data Monitoring Committee (Called Safety Monitoring Committee in this study).

An un-blinded safety committee will monitor clinical outcome in the included patients before each increasing dose.

### 9. Data Management and monitoring

#### 9.1 Case Report Forms

The Clinical Data Management System (CDMS) used for the eCRF in this study is "Web Form" ("Nettskjema") at University of Oslo. The setup of the study specific eCRF in the CDMS will be performed by the investigators.

The designated investigator staff will enter the data required by the protocol into the eCase report forms (eCRF). The Investigator is responsible for assuring that data entered into the eCRF is complete, accurate, and that entry is performed in a timely manner. The signature of the investigator will attest the accuracy of the data on each eCRF. If any assessments are omitted, the reason for such omissions will be noted on the eCRFs. Corrections, with the reason for the corrections will also be recorded.

After database lock, the investigator will receive a digital copy of the subject data for archiving at the investigational site.

#### 9.2 Source Data

Nettskjema will be the primary source of source data for the study and information from physical examinations will be recorded here. Additionally, relevant data from the hospital patient records will be recorded in the paper version of the study file or via Nettskjema. A single excel sheet is the source data for adverse events. The audiometry results will be transferred from the audiometer to K: sensitive. When the source data is in paper form, a digital copy will be taken using the Nettskjema secure photo app and stored in tsd. The hospital records will be updated with findings from study examinations where this is deemed relevant by the study staff.

To achieve this, the medical records of each patient will clearly describe at least:

- That the patient is participating in the study, e.g. by including the enrolment number and the study code or other study identification;
- Date when Informed Consent was obtained from the patient and statement that patient received a copy of the signed and dated Informed Consent;
- Results of all assessments confirming a patient's eligibility for the study;
- Diseases (past and current; both the disease studied and others, as relevant);
- Surgical history, as relevant;

- Treatments withdrawn/withheld due to participation in the study;
- Results of assessments performed during the study if relevant.
- Treatments (NR) given, changes in treatments during the study and the time points for the changes.
- Visits to the clinic / telephone contacts during the study, including those for study purposes only;
- Non-Serious Adverse Events and Serious Adverse Events (if any) including causality assessments if relevant.
- Date of, and reason for, discontinuation from study treatment;
- Date of, and reason for, withdrawal from study;
- Date of death and cause of death, if available;
- Additional information according to local regulations and practice.
- Kit number as well as the production codes of all flasks contained in a kit.
- Information regarding un-blinding procedures, contact numbers and reporting side effects.

The eCRF will be the source data for adverse events and self-reporting questionnaires will be filled out electronically through Nettskjema. For other data the hospital records will be the source data.

#### 9. 3 Study Monitoring

The investigator will be visited on a regular basis by the Clinical Study Monitor, who will check the following:

- Informed consent process
- · Reporting of adverse events and all other safety data
- Adherence to protocol
- Maintenance of required regulatory documents
- Study Supply accountability
- Facilities and equipment (example: laboratory, pharmacy, ECG machine, etc...) if applicable
- Data completion on the CRFs including source data verification (SDV).

The monitor will review the relevant CRFs for accuracy and completeness and will ask the site staff to adjust any discrepancies as required.

The institution's representatives (e.g. monitors, auditors) will be allowed access to source data for source data verification in which case a review of those parts of the hospital records relevant to the study will be required.

The study will be monitored according to GCP standards by OUS, Department of Research Support.

#### 9.4 Confidentiality

The investigator shall arrange for the secure retention of the patient identification and the code list in e-biobank. Patient files shall be kept for the maximum period of time permitted by each hospital. The study documentation (CRFs, Site File etc) shall be retained and stored during the study until 31.12, 2030 (the date defined in the REK application for the study). All information concerning the study will be stored in a safe place inaccessible to unauthorized personnel.

